A priori decision rules will be applied to select the intervention condition that is most effective and the simplest to undergo further testing in a subsequent RCT. Consistent with best practices for studies aiming to select the most effective combination of intervention elements using a factorial design, we will use a process of elimination rather than hypothesis-testing approach in applying our decision rules (Collins, 2018). In this approach, a series of criteria will be applied, and intervention elements that fail to meet minimum criteria for efficacy will be ruled out until the strongest set of elements remains (Collins, 2018). Because Type I error is less of a concern in this approach than Type II error, significance will be defined as $p < .10$.

Decision rules are based on co-primary and secondary outcomes and do not include intervention completion rates. This decision reflects both the type of intervention (texts are passively delivered) and pilot findings (no participants withdrew from the pilot), thus non-completion rates are not expected to be a concern.

Decision rules will be as follows:

1. We will first examine main effects for PTSD and HED in a model without interaction terms. We will retain any enhancements for further consideration in Step 2 that have significant negative main effects for both outcomes. If none exist, we will retain enhancements with significant negative main effects on PTSD or HED alone.

2. We will then examine interaction effects (framing x growth mindset x time) for PTSD and HED among any enhancements with significant negative main effects. If there is one or more negative interaction terms, we will examine linear contrasts among the combinations of enhancements that are part of the interaction to determine whether adding specific enhancements leads to improvement. If this does not yield a clear conclusion in terms of the combination of effects to select, we will examine the direction and magnitude of the main and interaction effects for these conditions on secondary outcomes and participant satisfaction data. If there are no negative interaction terms, we will select any enhancements that had significant main effects and no evidence for negative impacts on outcomes.

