3. If there are no positive significant interactions or main effects for either PTSD or HED, we will repeat step 1 and 2 with other co-primary and secondary outcomes in the following order: alcohol use consequences (SIP), typical weekly alcohol consumption (DDQ), depression (DASS), and anxiety (DASS).
4. If effect sizes across conditions do not differ significantly from control (no framing, simple reminder), we will choose the control given that it is the simplest condition.

Power

The co-primary outcomes for this study are HED and PTSD symptom severity. Power calculations were conducted for HED, as its lower expected average values and non-normal distribution was expected to generate a more conservative estimate of sample size relative to PTSD symptom severity. Considering a base rate of 5.93 episodes of HED per week (based on our pilot data) and $\alpha = .05$, we determined that a sample size of $N = 500$ ($n = 75$ per condition; n

= 150 per comparison) would yield $>.80$ power to detect an 18% or greater difference in number of HED episodes between any two conditions (i.e., count ratio of 0.82).

Decision rules were revisited in response to reviewer feedback when submitting our protocol for potential publication. We realized that our original approach was not fully aligned with our power analysis or our overarching goal of identifying the most efficacious *and* simplest condition. We realized that a process-of-elimination approach starting with main effects was more in line with our goal (rather than first testing the hypothesis that the combination of growth mindsets and loss-framing would be the most efficacious condition). We thus altered our decision rules from what was originally submitted to the funder and will be testing main effects (rule 1) first, followed by interaction effects (rule 2). Further, given our process of elimination approach (vs. hypothesis testing), a *p*-value cut-off of 0.10 is appropriate (Collins, 2018). The power analysis was reviewed with these changes, and we anticipate having $>.80$ power to detect even smaller main effects (i.e., a count ratio of .89).

Assessing Differences by Condition

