We will use an intent-to-treat approach to analyze results and retain all available data. For each outcome, we will explore change over time by condition visually, using within-group pre-post effect sizes ($d = (M_{post} - M_{pre})/S_{dif}$), and in generalized linear mixed effects models. In mixed-effects models, we will test main effects for each enhancement (i.e., framing enhancements with no framing as the reference, growth mindset with no growth mindset as the reference) and time (baseline, post, 1-month, 3-month), and a 3-way interaction term for framing \times growth mindset \times time. We will evaluate the need for random effects for time, different specifications for time (e.g., linear, quadratic), and count regression forms of the mixed-effects model (e.g., Poisson, negative binomial, zero-inflated).

Missing Data

Mixed-effects modeling should yield unbiased estimates in the presence of missing data assuming data are missing at random—that is, missingness is only related to observed data, but not the unobserved data. We will explore missing data patterns according to baseline (time-fixed) values of variables and consider the inclusion of additional covariates that show strong associations with missingness above and beyond any other planned covariates. Should sensitivity analyses suggest that the findings may be dependent on unobserved data, we will consider the need for approaches to missing data (e.g., using the pattern-mixture approach to combine effects across missing data patterns to yield unbiased results).

References

Bedard-Gilligan, M. A., Dworkin, E. R., Kaysen, D., Ojalehto, H. J., Stappenbeck, C. A., & Lindgren, K. P. (2022). A pilot study on the feasibility, acceptability, and preliminary efficacy of a brief text message intervention for co-occurring alcohol misuse and PTSD symptoms in a community sample. *Journal of Anxiety Disorders*, 91, 102615.

Blevins, C. A., Weathers, F. W., Davis, M. T., Witte, T. K. & Domino, J. L. (2015). The posttraumatic stress disorder checklist for DSM-5 (PCL-5): Development and initial psychometric evaluation. *Journal of Traumatic Stress*, 28, 489–498. DOI: 10.1002/jts.22059

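### Rule 2 abandons the main-effect selection on the sign of an interaction term, with no significance threshold stated

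*Combined protocol and SAP*

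**What the plan says.** All references are to the combined protocol and SAP.

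- **Decision Rules, introduction.** Significance is set at p < .10 for the selection process.
- **Rule 1.** Enhancements go forward only if their main effects are both significant and negative. Negative means benefit here, since lower HED and PTSD scores are better.
- **Rule 2, scope.** The next check is of "interaction effects (framing x growth mindset x time) for PTSD and HED among any enhancements with significant negative main effects".
- **Rule 2, switch.** "If there is one or more negative interaction terms, we will examine linear contrasts among the combinations of enhancements". If the contrasts do not settle the choice: "If this does not yield a clear conclusion in terms of the combination of effects to select, we will examine the direction and magnitude" of effects on secondary outcomes, together with satisfaction data.
- **Rule 2, other branch.** "If there are no negative interaction terms, we will select any enhancements that had significant main effects and no evidence for negative impacts on outcomes".
- **Rule 3.** It applies when there are "no positive significant interactions or main effects for either PTSD or HED".
- **Assessing Differences by Condition.** The model has reference-coded main effects, time at four occasions "and a 3-way interaction term for framing" by growth mindset by time. Whether time is linear, quadratic or otherwise is left to be evaluated.
- **Power.** The rules were revised so that selection starts from main effects and agrees with the power analysis. Power above .80 is claimed for main effects at a count ratio of .89.

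**The concern.** Rule 1, rule 3 and the last sentence of rule 2 all use the word *significant*. The switch in rule 2 does not. Taken as written, the main-effect selection survives only if no interaction estimate is below zero. With no interaction in truth, each estimate falls below zero half the time, and several are inspected across two outcomes.

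Once the switch fires, the decision moves from margins of 150 or more per level to single cells of 75–83. Enhancements that passed the better-powered test are then re-decided by weaker comparisons, usually because of chance signs. That works against the reason the Power section gives for revising the rules. The selected condition goes forward to a further RCT, so the gate should be unambiguous before analysis.

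**Working it through.** **Inputs.** From the Power section: HED base rate 5.93, N = 500, 75 per condition, count ratios .82 and .89. From Decision Rules: p < .10, taken as two-sided because sidedness is not stated. Cells: 75 as stated, or 500/6 = 83.3. Framing level: 2 × 75 = 150, or 500/3 = 166.7. Assumed because the documents do not give them: Poisson variance and an HED–PTSD correlation of 0 to .5.

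**Step 1. Reproduce the plan's power.** For a count ratio CR with n per group, SE² = 1/(5.93n) + 1/(5.93n·CR), and power = Φ(|ln CR|/SE − z).

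- CR .82, n = 75, alpha .05: SE = .0706, Φ(.1985/.0706 − 1.960) = **.802**. This agrees with the stated figure.
- CR .89, n = 166.7, alpha .10: SE = .0464, Φ(.1165/.0464 − 1.645) = **.808**. This agrees with the revised figure. At n = 150 it is .770.

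**Step 2. Power after the switch.** Same formula, alpha .10, one cell against another.

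| Count ratio | n = 75 | n = 83.3 |
|---|---|---|
| .89 | .517 | .553 |
| .82 | .878 | .906 |

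**Step 3. How often the switch fires with no interaction.** Interaction estimates are drawn as multivariate normal with mean zero. The two framing terms correlate .5 (shared no-framing reference), and categorical time terms correlate .5 (shared baseline). The simplest case can be done by hand. With one framing and linear time there is one term per outcome. Independent outcomes give 1 − .5² = 75%. At outcome correlation .5, the chance that both are positive is 1/4 + arcsin(.5)/(2π) = 1/3, giving 67%. The last column counts a term only if it is negative and p < .10, which is 5% per term.

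| Retained with growth mindset | Time | Any negative sign | Any negative term at p < .10 |
|---|---|---|---|
| One framing | Linear | 67–75% | 9–10% |
| One framing | Categorical | 88–94% | 20–22% |
| Both framings | Linear | 82–89% | 15–17% |
| Both framings | Categorical | 96–99% | 32–36% |

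These are shares of trials in which a framing and growth mindset are both retained, with HED and PTSD both checked. If one term on one outcome is inspected, the sign rule fires in 50%.

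**Step 4. What happens after it fires.** Rules 1 and 2 were simulated with additive effects: one active framing plus growth mindset, the same standardised effect on PTSD, linear time, outcome correlation 0 or .3, and 75 or 83.3 per cell. The combination is confirmed if it beats each single-enhancement cell at p < .10.

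| Both contrasts confirmed, given the switch fired | CR .89 | CR .82 |
|---|---|---|
| On HED alone | 48–57% | 80–87% |
| On the outcome that triggered the switch | 75–80% | 97–98% |
| Each contrast met on either outcome | 81–85% | 98–99% |

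The switch fires in about 38–43% of all simulated trials at .89 and 68–74% at .82, because step 1 must first retain both kinds of enhancement.

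**The case against.** **The threshold may be implied.** The introduction to the rules defines significance as p < .10, and rule 3, which covers the case where rules 1 and 2 find nothing, speaks of significant interactions. The authors may well have meant it throughout. This stands as a plausible reading, but rule 2 does not say it. The rate would still run from 9–10% to 32–36% depending on the framings retained and a time coding not yet fixed.

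**The check mixes two standards.** Rule 2 sets no p-value for the contrasts either. If direction alone is enough, the combination beats both single-enhancement cells in over 99.9% of HED-triggered trials in the additive .89 example. If p < .10 applies throughout, the HED term fires in about 5% of trials where both enhancements pass step 1, and both contrasts then confirm in over 99%. This also stands: the loss in step 4 arises when the switch is read literally and the contrasts are held to p < .10.

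**Stronger readings are not supported.** A reader might infer that over 80% of trials switch by chance. That needs both framings retained, or categorical or quadratic time; one framing with linear time gives 67–75%, and the share of all trials is lower. A reader might also infer that real effects are mostly lost, from the roughly 43–45% joint HED confirmation among trials passing step 1 at .89. That figure is not conditional on the switch. A negative interaction means the combination did better than additive, which favours the contrasts, so confirmation after switching is higher. Failure to confirm leads to secondary outcomes and satisfaction data, not to rejection. At .82 the cell contrasts are adequately powered.

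**Conclusion.** The gap is real and worth closing before analysis. Rule 2 states no evidence standard for leaving the main-effect selection. Followed literally under no interaction, it leaves that selection in about 67–99% of trials where a framing and growth mindset both reach step 2. At the plan's own main-effect target of .89, it replaces a framing test with about 77–81% power by HED cell contrasts with about 52–55%.

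The consequence is moderate. It is largest at .89 on HED alone (about 48–57% joint confirmation), smaller on the triggering outcome (75–80%), and nearly absent there at .82 (97–98%). The fallback for unclear contrasts also has no threshold, so a main effect already shown on a co-primary outcome could be re-decided on weaker evidence.

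These sizes rest on Poisson variance, an assumed outcome correlation, additive effects and contrasts judged at p < .10. Poisson is used because it reproduces both stated power figures; overdispersion would lower the power of every comparison.

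**What to change.** Reword rule 2 along these lines: *For each of PTSD and HED, fit the model with all lower-order terms and carry out one joint test of the framing × growth mindset × time terms for the enhancements retained in step 1. Examine contrasts among combinations only if that test is significant at p < .10 for either outcome. Otherwise select the step 1 enhancements, subject to the existing condition on negative impacts.* State also what standard the contrasts must meet.

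Report the operating rate. With two independent outcomes the gate fires under no interaction in 1 − .90² = 19% of trials, or about 18% at outcome correlation .5. If about .10 overall is wanted, use .05 per outcome: 1 − .95² = 9.75%. The joint test fires less often than term-by-term testing with both framings under categorical time (32–36%), but not under linear time (15–17%). Its main gain is a rate that does not depend on the time coding.

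The cost is one sentence and one model comparison per outcome. A weak real interaction will be followed up less often. The joint test is not directional, so the sign must be read from the contrasts.

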Measures will be exclusively self-report questionnaires to minimize participant burden and have practical remote study procedures. Demographics including age, race/ethnicity, gender, income/work status, weight (for blood-alcohol-concentration calculation), verification of cell phone ownership and willingness to receive messages, certification of English fluency, and current residential zip code (to verify WA State residency) will be assessed at screening. Trauma exposure will be assessed at screening and at 3-month follow-up (intervening trauma exposure). We will use the Life Events Checklist (LEC; Weathers et al., 2013), a 16-item measure that queries on lifetime experience of commonly reported traumatic events (e.g., sexual assault, natural disasters) and identifies the most impactful, worst event in the person's lifetime.

Co-Primary Outcome Measures. Co-primary outcome measures will be given at screening or baseline and at all follow-ups. Power calculations were based on the heavy episodic drinking outcome (see power analysis section).

Drinking behavior will be assessed via well-validated measures that provide details on drinking patterns. Heavy episodic drinking over the past month (HED: 4/5 or more drinks per single occasion for women/men) will be assessed with the Quantity Frequency scale (QF; Baer, 1993) that asks about past month peak drinking occasion, how many drinks were consumed on that occasion, and over how many hours the drinks were consumed. Typical weekly alcohol consumption will be assessed using the Daily Drinking Questionnaire (DDQ; Collins et al., 1985); participants will report the number of drinks they typically consume each day. Negative

alcohol-related consequences will be assessed via the Short Index of Problems (SIP; Miller et al., 1995), which corresponds with longer measures of drinking consequences (Forcehimes et al., 2007).

PTSD symptom severity will be assessed using the PCL-5 (Weathers et al., 2013). The PCL-5 uses the event selected as the “worst” on the LEC to index PTSD symptoms to a target trauma. The PCL-5 is commonly used and has good test-retest reliability ($rs = .82\text{-.84}$) and strong convergent validity ($rs = .85\text{-.87}$) with other PTSD measures (Blevins et al., 2015).

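### One power figure (more than .80 at a count ratio of .89) covers two factors with different n, leaves framing no room for overdispersion, and uses a base rate whose unit conflicts with the outcome

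*Combined protocol and SAP*

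**What the plan says.** The Power section bases its calculation on HED: "Considering a base rate of 5.93 episodes of HED per week (based on our pilot data", with alpha .05. It gives "a sample size of $N = 500$ ($n = 75$ per condition" and 150 per comparison, and claims more than .80 power for an 18% "difference in number of HED episodes between any two conditions (i.e., count ratio of 0.82".

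The same section then explains that main effects will now be tested first at p < .10, and anticipates more than .80 "power to detect even smaller main effects (i.e., a count ratio of .89". That sentence gives no n, sidedness, count model, dispersion or attrition, and does not separate the two factors.

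Other sections bear on the figure:
- Decision Rules, on the threshold: "Type I error is less of a concern in this approach than Type II error, significance will be defined as $p < .10". On Step 1: "We will first examine main effects for PTSD and HED in a model without interaction terms".
- Assessing Differences by Condition sets the contrasts: "framing enhancements with no framing as the reference, growth mindset with no growth mindset as the reference". It plans mixed models over four time points and leaves the count form open, naming negative binomial and zero-inflated options.
- Co-Primary Outcome Measures defines the outcome: "Heavy episodic drinking over the past month (HED: 4/5 or more drinks per single occasion for women/men".

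**The concern.** In a 3 x 2 design each framing level holds a third of the sample and each mindset level holds half, so at a given ratio the framing contrasts have less power. A single figure hides this.

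The plan ranks Type II error above Type I error, and Step 1 drops enhancements whose main effects on PTSD and HED are not significant. Power for each factor is therefore the figure a reader needs. HED is not the only route to retention: Step 1 can retain on PTSD alone, and Step 3 moves on to other outcomes. This limits the consequence.

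The inputs also raise doubts. The Power section itself calls HED non-normal but states no dispersion, and its base rate covers a different period from the outcome.

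**Working it through.** **Inputs.** Mean 5.93, ratios .82 and .89, 75 per condition and N = 500 (Power); p < .10 (Decision Rules); contrasts (Assessing Differences by Condition). I read 150 per comparison as 75 + 75, because that sentence compares two conditions. Assumed, because not stated: two-sided test, Poisson variance, one time point.

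**Formula.** Wald test on the log count ratio RR with n per group and overdispersion k:

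SE² = [1/5.93 + 1/(5.93 × RR) + 2k] / n; power = Φ(|ln RR|/SE − z).

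**Step 1: the plan's .82.** With k = 0, 75 vs 75, alpha .05:
- SE² = (.1686 + .2057)/75, so SE = .0706
- |ln .82|/SE = .1985/.0706 = 2.809
- power = Φ(2.809 − 1.960) = .802

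The detectable ratio at .80 power is .8205. A one-sided test would give .840, so the printed .82 supports the two-sided, Poisson, single-time-point reading.

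**Step 2: the same method at .89, p < .10.** Here 1/5.93 + 1/(5.93 × .89) = .3581 and |ln .89| = .1165.

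| Contrast | n per level | Power at .89 | Detectable ratio at .80 |
|---|---|---|---|
| Framing, 75 per condition | 150 | .770 | .8855 |
| Framing, all 500 | 166.7 | .808 | .891 |
| Growth mindset, 75 per condition | 225 | .899 | .906 |
| Growth mindset, all 500 | 250 | .924 | .911 |

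A simulation of 200,000 Poisson trials gave .770, .809 and .899 for the first three rows. Other two-sided formulas at 150 per level give .770 to .785, all below .80.

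**Step 3: n that framing needs.** .3581 × (2.4865/.1165)² = 163.04 per level with unrounded inputs. Times 3 this is 489.1, so 490 of 500. The stated 75 per condition means 6 x 75 = 450.

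**Step 4: room for overdispersion.** The largest k that keeps .80 on this method is:
- the .82 claim: .001 at 75 per condition, .022 at 83.3 (500/6)
- framing at .89: none at 150 per level, .004 at 166.7
- growth mindset at .89: 2k = n × (.1165/2.4865)² − .3581, so k is about .07 at 225 and .10 at 250

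**Step 5: the unit.** The tolerable k depends on the unit of 5.93 (single time point throughout):
- Weekly count, assuming at most one episode a day: variance is at most 5.93 × 1.07 = 6.35, so k is at most (6.35 − 5.93)/5.93² = .012. Framing then has .747 (150) or .785 (166.7). A count less variable than Poisson would give more.
- Converted to a month, mean 5.93 × 30/7 = 25.4: framing keeps .80 up to k of about .12 (150) or .14 (166.7).
- If 5.93 is really a past-month count: assumed k of .1, .2 or .5 gives framing .605, .498 or .337 at 150.

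**Step 6: repeated measures.** Framing at 150 per level, ratio .89, with Poisson noise within person and an assumed between-person variance on the log scale. Averaging over m times replaces .3581 by .3581/m and 2k by twice that variance. If baseline is one of four outcome times and there is no interaction term, the log effect is also multiplied by .75.

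| Between-person variance (assumed) | 0 | .1 | .2 |
|---|---|---|---|
| Three follow-ups | .994 | .811 | .631 |
| Four times, baseline included | .97 | .63 | .45 |

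The columns for .1 and .2 do not apply if the weekly cap in Step 5 holds.

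**The case against.** The strongest reply is that the printed .89 is simply the framing result. The detectable ratio at 150 per level is .8855, which rounds to .89, just as .8205 was printed as .82. The plan may thus have quoted its less well powered factor and hidden nothing. This largely stands. What remains is that rounding went in the favourable direction, so power at the printed ratio is .770.

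Second, the .89 sentence names no n; the 75 per condition belongs to the .82 calculation. With all 500 the claim is true for both factors. Participants are also randomised after completing baseline, and all available data are kept, so a missed survey does not remove a person from the analysis. This stands too: the figure of 490 is not a dropout limit for the planned model. But nothing explains how 450 and 500 relate.

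Third, other readings exceed .80 for framing at 150 per level: .865 with one-sided p < .10, .811 if 5.93 is taken as the lower of the two counts, and up to .994 with three follow-ups. The plan states none of these, and one-sided testing does not match the .82 figure.

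A reader might infer that the trial is underpowered for framing, or that the .89 claim is false. The documents do not support either. The .770 belongs to a single-time-point Poisson check, the gap is .0045 in the ratio, and the analysis model could move power in either direction.

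**Conclusion.** The point holds in a limited form. One figure is stated for two factors whose power at .89 differs by about 12 to 13 percentage points. On the method that recovers the plan's own .82, framing falls 3 points short of .80 at 75 per condition and passes by less than 1 point if all 500 are analysed. Growth mindset meets the claim at either n. The framing shortfall is small and probably comes from rounding.

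The inputs matter more. At 75 per condition the .82 ratio, and at any n up to 500 the .89 ratio for framing, reproduce only with essentially no overdispersion, although the plan itself foresees overdispersed or zero-inflated counts. The base rate is weekly and the outcome monthly, and no attrition figure connects 450 to 500. The size of the shortfall rests on two-sided testing, Poisson variance and one time point; the unit conflict and the unlinked sample sizes rest on no assumption. Actual power is indeterminate from the documents.

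**What to change.** Revise the paragraph on power as follows:
1. Reconcile the HED unit, weekly or past month, between Power and Co-Primary Outcome Measures.
2. Recalculate from the pilot mean and variance on that unit, allowing for overdispersion, for the Step 1 repeated-measures model and its contrasts. State the within-person correlation and whether baseline is a covariate or an outcome time.
3. State sidedness, the n analysed, and the attrition assumption that links 500 to 6 x 75 = 450.
4. Replace the single figure with separate detectable ratios for framing (each level against no framing) and growth mindset, not rounded in the favourable direction.

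Keep N and the decision rules unchanged. The cost is one recalculation from the pilot data and one reworded paragraph, with no extra participants. The downside is that the stated detectable effect for framing may become slightly less favourable.

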Once the participants complete the baseline assessment, they will be randomized using a web-based custom program. Participants are entered into the program by the project coordinator. Randomization will use stratified permuted block randomization in 8 strata with three stratified variables: PTSD severity (PCL-5 scores of 33-60 vs. ≥ 61), risk of alcohol use disorder (AUDIT scores < 20 vs. ≥ 20), and gender identity (male vs. any other gender identity). Within strata, conditions assignments are based on prior assignments to ensure balanced numbers across intervention conditions. Stratification aims to control representation of factors commonly related to intervention response across conditions.

Starting the Monday following randomization, intervention texts will be sent 3 days a week (Tuesday, Wednesday, Friday) for 4 consecutive weeks. Each participant will receive 2 texts, back-to-back, each day based on intervention condition (see below). The participant chooses what time of day they receive the texts.

A post-intervention assessment will be emailed the day after the last text has been received, and a follow-up survey will be sent 1-month and 3-months post intervention. Regular reminders will be sent to maximize completion of the follow-up surveys. All measures, procedures, and intervention delivery are done via automated text message or self-report computerized survey: study investigators and staff are not aware of individual participant intervention conditions.

Participants will be compensated for completing baseline and follow-up assessments. Compensation will be \$20 at baseline, \$25 at post, \$30 at 1-month, and \$35 at 3-month follow-up, given as Amazon gift cards. Gift card drawings after each of the follow-up assessments (five, \$50 Amazon gift cards) will be used to further encourage assessment completion. Participants will not be compensated for screening or for receiving messages.

Fraud Detection

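### The Step 1 main-effect models name none of the three randomisation strata; if the strata are left out, those tests are conservative and give up about 1 to 5 points of power that could be had at no cost.

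*Combined protocol and SAP*

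**What the plan says.** Under Procedures: "Randomization will use stratified permuted block randomization in 8 strata with three stratified variables". The factors are PCL-5 (33-60 vs 61 or more), AUDIT (below 20 vs 20 or more) and gender identity (male vs any other). The stated purpose is: "Stratification aims to control representation of factors commonly related to intervention response across conditions".

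Under Decision Rules, Step 1 reads: "We will first examine main effects for PTSD and HED in a model without interaction terms". The significance threshold there is p < .10, justified as follows: "Because Type I error is less of a concern in this approach than Type II error".

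Under Assessing Differences by Condition: "In mixed-effects models, we will test main effects for each enhancement". The other terms listed are time and the framing by mindset by time interaction. No stratum appears.

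The only hint of other covariates is in Missing Data, which would consider adding predictors of missingness "above and beyond any other planned covariates". No section lists those planned covariates, so the plan leaves open whether the strata are among them.

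**The concern.** A trial that stratifies on prognostic factors normally puts them in the model. Stratified allocation removes most of the between-arm variation due to those factors, so the estimated effect varies less from trial to trial than it would under simple randomisation. A model without the factors cannot see this. It leaves their variance in the error term, reports too large a standard error, and the test rejects less often than its nominal level.

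This matters most in Step 1. With no interaction terms, each enhancement effect there is a between-person comparison, and Step 1 decides which enhancements reach Step 2. The plan relaxed its threshold to .10 because missing a useful enhancement is the worse error. A test that in fact runs below .10 works against that choice.

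**Working it through.** **The plan's own power figures.** Inputs from the Power section: 5.93 HED episodes, 75 per condition, count ratio 0.82, alpha .05 (two-sided assumed). With Poisson variance, SE = sqrt(1/(75 × 5.93) + 1/(75 × 5.93 × 0.82)) = 0.0706. Then |ln 0.82|/SE = 0.1985/0.0706 = 2.81, and power = Φ(2.81 − 1.96) = .802, which reproduces the stated figure of over .80.

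For the revised main-effect claim (count ratio 0.89, alpha .10) the same formula gives:
- framing: .770 at 150 per level and .806 at 166 per level (500/3);
- mindset: .899 at 225 per level and .924 at 250 per level.

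These figures allow for no overdispersion. The framing contrasts therefore sit near .80 and the mindset contrast near .90.

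**Effect of leaving the strata out.** Let R² be the share of variance in the person-level mean outcome that the strata explain. The documents give no value; 5%, 10% and 20% are assumed. Let r = sqrt(1 − R²), z = 1.645 (two-sided .10) and d = 1.645 + 0.842 = 2.487, which is 80% nominal power.

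- Reported SE / true SE without strata = 1/r
- True size without strata = 2(1 − Φ(z/r))
- Power without strata = Φ((d − z)/r)
- Power with strata = Φ(d/r − z)

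Worked for R² = .10: r = 0.9487. Size = 2(1 − Φ(1.734)) = .083. Power without = Φ(0.887) = .813. Power with = Φ(0.976) = .835.

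| R² | SE too wide by | True size | Power without | Power with | Gain (points, unrounded inputs) |
|---|---|---|---|---|---|
| .05 | 2.6% | .091 | .806 | .818 | 1.2 |
| .10 | 5.4% | .083 | .813 | .835 | 2.3 |
| .20 | 11.8% | .066 | .827 | .872 | 4.5 |

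Outside this range, R² = .02 gives 0.5 points and R² = .30 gives 6.5. With nominal power .90 instead of .80, the gains at R² .05, .10 and .20 are 0.7, 1.3 and 2.4 points.

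**Simulation, linear model.** N = 500, six arms, 8 strata, four visits, random intercept; assumed permuted blocks of 6 and intraclass correlation .6; 4,000 runs per cell; mindset main effect; R² .05/.10/.20.
- Complete data: size without strata .091/.080/.068, with strata .099/.098/.097. Power rises from .799 to .812, .822 to .843 and .823 to .871.
- With an assumed 25% dropout by 3 months, the gains are 1.0, 2.3 and 4.3 points.

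A separate simulation with 6,000 runs per setting gave 1.1, 2.5 and 4.7 points for framing and 1.2, 2.3 and 4.6 for mindset.

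**Counts.** A quasi-Poisson simulation (3,000 runs per setting, count ratio 0.85, power near 80-85%) gave gains of 1.1 points at a person-level R² of .06 and 4.2 points at .16. Size without strata was .098 and .080; with strata it was .108 and .112, so a little of the count-model gain reflects a slightly liberal adjusted test.

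**Step 2.** For framing by mindset by linear time (600 runs per R²), the standard error is 0.0620 with and without the strata. Baseline is one of the outcome time points, so stable differences between people largely cancel.

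**The case against.** Five points can be made against this.

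1. Power without the strata is still at or slightly above the planned .80, so the plan's power statement is not undermined. This stands: what is lost is a gain the design has already paid for.
2. A range of 1 to 5 points does not fit every contrast. This also stands. For mindset, at the plan's count ratio of 0.89, power is nearer .90 and the gain is about half as large.
3. R² differs by outcome. For PTSD one stratum is a cut of the outcome's own baseline score, and baseline is an outcome row. Illustrative assumptions gave R² of .14 to .44 for the four-visit mean, so the PTSD gain could exceed 5 points. This affects the size and not the direction.
4. The strata may already be among the unlisted planned covariates. If so, nothing is lost and listing them settles the matter.
5. Three factors are not the same as 8 strata. In simulation, three additive factors and full 8-stratum terms performed the same, so the simpler form suffices.

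**Conclusion.** The concern holds, as a modest and free improvement in efficiency. As written, the plan names no stratum in its models. If that is followed, the Step 1 tests are conservative (true size about .066 to .091 at a nominal .10) and forgo 1.2 to 4.5 points of power for a contrast planned at .80.

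This rests on an assumed R² of .05 to .20, a two-sided test, and a model that carries between-person variance through a random intercept or overdispersion. A plain Poisson fit without either would be badly anti-conservative whether or not the strata are included. The treatment comparison is not biased, Type I error is not inflated, and no gain is claimed for the Step 2 three-way test.

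**What to change.** Add to Assessing Differences by Condition: the Step 1 main-effect model for each outcome, and its repeat in Step 3, includes as fixed effects the three randomisation factors as recorded at randomisation: PCL-5 (33-60 vs 61 or more), AUDIT (below 20 vs 20 or more) and gender identity (male vs any other). List any other planned covariates in the same place. For the PTSD outcome, say how the PCL-5 factor enters, since baseline PCL-5 is also an outcome row and a constant effect over time may not fit. The factors may stay in the Step 2 models for consistency.

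The cost is one dated sentence and three degrees of freedom out of about 500 participants. All three factors are known for every randomised participant. The one constraint is timing: the document is dated 03/12/2024 and expects data collection to end by April 2024, so the change should be dated and should state that outcomes had not yet been examined by condition. If they had been, that should be said instead.
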